8.6.1.1 Supportive Management Recommendations for Rash

LY3214996 may cause rash. To help mitigate the rash, the following recommendations are provided. These recommendations are intended to be a guideline for the investigator and should not replace the investigator's best judgment.

Once a patient starts treatment on the study, patients will be instructed to initiate the use of a moisturizer with no scents added. In addition, patients will be directed to limit sun exposure or to apply sunscreen protection before going outdoors (PABA-free, SPF 15 or higher) if appropriate. A prescription for topical antimicrobials and steroidal agents based on institutional practice or guidelines will be provided by the investigator(s)/nurse(s) to the patient. The patient will be instructed to immediately fill the prescription for the topical agents and to start it immediately at the first onset of a Grade 1 rash. If the rash escalates further, then the patient will be instructed to call the study investigator(s)/nurse(s) and additional interventions per institutional practice or guidelines for oral steroids, oral antimicrobials, or dose reductions per investigator discretion may be implemented. Rash management recommendations are listed in [Table 8.1](#).

Table 8.1 Management Recommendations for Skin Reactions

Toxicity Grade	Management Recommendations
Grade 1	
 Administer topical clindamycin 1% or topical hydrocortisone 1% in lotion base twice daily to affected areas until resolution of reaction.
Grade 2	
 Administer topical clindamycin 2% and topical hydrocortisone 1% in lotion base twice daily to affected areas until resolution of reaction. If clinically appropriate in the opinion of the investigator, administer oral minocycline or doxycycline 100 mg twice daily (or equivalent), for a minimum of 4 weeks and continue using for as long as rash is symptomatic.
Grade 3	
 Temporarily withhold LY3214996 and abemaciclib until symptoms resolve to Grade ≤ 2 or pre-treatment baseline. Treatment may be held for up to 21 days Continue ongoing rash treatment. Following improvement to Grade ≤ 2, re-administer LY3214996 with a dose reduction of 1 dose level. Abemaciclib does not require a dose reduction If symptoms do not recur for another treatment cycle, the LY3214996 dose may be re-escalated to the previous dose level.
Grade 4	
 Immediately and permanently discontinue treatment with LY3214996 and abemaciclib. Continue ongoing rash management treatment. Provide intravenous hydration or electrolyte replacement if needed. Request dermatologist advice if needed.

8.6.1.2 Supportive Management for Diarrhea

Patients should receive instructions on the management of diarrhea. In the event of diarrhea ([Appendix 4](#)), supportive measures should be initiated as early as possible. These include the following:

- At the first sign of loose stools, the patient should initiate anti-diarrheal therapy (for example, loperamide) and notify the investigator/site for further instructions and appropriate follow-up.
- Patients should also be encouraged to drink fluids (for example, 8 to 10 glasses of clear liquids per day).
- Site personnel should assess response within 24 hours.

- If diarrhea does not resolve with anti-diarrheal therapy within 24 hours to either baseline or Grade 1, abemaciclib should be suspended until diarrhea is resolved to either baseline or at least Grade 1.
- When abemaciclib resumes, dosing should be adjusted as outlined in [Appendix 4](#).

In severe cases of diarrhea, the measurement of neutrophil counts and body temperature and proactive management of diarrhea with antidiarrheal agents should be considered.

If diarrhea is severe (requiring IV rehydration) and/or associated with fever or severe neutropenia, broad-spectrum antibiotics such as fluoroquinolones must be prescribed. Patients with severe diarrhea or any grade of diarrhea associated with severe nausea or vomiting should be carefully monitored and given intravenous fluid (IV hydration) and electrolyte replacement.

8.6.1.2.1 *Loperamide*

Based on the toxicities observed with abemaciclib loperamide, 2 mg orally, may be administered with the first dose of abemaciclib daily. If the daily dose of loperamide is not taken with the first dose of abemaciclib, it should be taken after the first loose stool. Patients may take an additional 2-mg-dose (1 capsule/tablet) of loperamide after each loose stool up to a maximum of 16 mg (8 capsules/tablets) per day (including doses taken with abemaciclib). In the event a patient experiences Grade 2 diarrhea (4 to 6 loose stools per day above baseline) despite loperamide, a dose reduction (–1 level) of abemaciclib can be considered before additional doses of loperamide are taken. If diarrhea recurs within 24 hours despite a dose reduction, additional doses (2 mg each) of loperamide may be taken at the investigator’s discretion. Loperamide may be discontinued 28 days after initiation of abemaciclib therapy at the investigator’s discretion. Loperamide dose can be omitted if the abemaciclib dose is omitted for a reason other than diarrhea. Loperamide administration, including dose adjustments (increases and/or decreases) and changes for indicated use, will be captured on the electronic case report form (eCRF). If a patient experiences constipation or other symptoms related to loperamide dosing (for example, abdominal cramping), the investigator may reduce/stop the patient’s dosing of loperamide. If a patient does not have a bowel movement for ≥ 36 hours, loperamide is to be suspended until bowel movements resume. If loperamide administration resumes, the dose may be adjusted (e.g., once every other day) at the investigator’s discretion. Investigators should take into account the patient’s history and/or risk of constipation when considering increases in loperamide dosing.

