tumors with overactivated MAPK pathway identified via pathogenic alterations in *BRAF*, *RAF1*, *MEK1/2*, *ERK1/2*, and *NF1*.

Expected overlapping toxicities of the combination include nausea, vomiting, fatigue, diarrhea, decreased appetite, blood creatinine increase, and alanine aminotransferase increased. Though rash is not considered an overlapping toxicity, an increased incidence of maculo-papular rash and dermatitis acneiform was observed in the combination during dose escalation of the phase 1 JUAB study.

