8.3 Dosage Modification

Please refer to [Appendix 4](#) for dose adjustment guidelines.

Study therapy may be held up to 3 weeks to allow sufficient time for recovery. Patients who do not recover from drug-related toxicity to \leq grade 1 within 3 weeks will be discontinued (except alopecia, fatigue, skin rash, elevated creatinine, nausea, vomiting, constipation or diarrhea that can be controlled with treatment). If a dose adjustment is made, the patient must be maintained at the reduced dose level for all remaining cycles.

For the purposes of dose modification, the investigator must first assess if the toxicity is considered at least possibly due to one of the study drugs, and must then apply the study drug-specific dose-modification guidelines accordingly. If the toxicity is not clearly attributable to either individual study drug, then the causality should be attributed to both study drugs. Dosing interruptions of any study drug are permitted for reasons not related to study treatment (for example, minor surgery, unrelated medical events, patient vacation, and/or holidays). The reason for interruption should be documented on the CRF.

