Recurrent in the context of dose interruptions and delays refer to the same event occurring within the next 8 weeks (as measured from the stop date of the first event). This does not include events in the same class (for example, neutropenia followed by anemia 1 month later).

As a general approach, based on the **risk/benefit balance assessment per the investigator**: for a patient who experiences a new episode of Grade 3 hematological toxicity after more than 8 weeks following the last episode of **same** Grade 3 hematological toxicity, the investigator may consider resuming the patient on the same drug dose if the patient satisfies the following conditions:

- The patient showed stable hematological counts (\leq Grade 2) during that time frame
- In the absence of any infectious sign or risk factor
- The patient is getting benefit from study treatment.

Non-Hematologic Toxicity:

Nausea**	Abemaciclib	LY3214996
\leq Grade 1	No change in dose.	No change in dose.
Grade 2	Hold* until \leq Grade 1. Resume at same dose level.	Hold* until \leq Grade 1. Resume at same dose level.
Grade 3	Hold* until \leq Grade 1. Reduce by 1 dose level.	Hold* until \leq Grade 1. Reduce by 1 dose level.
*Patients requiring a delay of all protocol therapy > 3 weeks due to toxicity should go off protocol therapy. ** After optimal anti-emetic therapy. Please refer to Section 8.6.1 . Use of prophylactic or scheduled antiemetics are recommended in future cycles for patients experiencing grade 2 or higher nausea.		

Vomiting**	Abemaciclib	LY3214996
\leq Grade 1	No change in dose.	No change in dose.
Grade 2	Hold* until \leq Grade 1. Resume at same dose level.	Hold* until \leq Grade 1. Resume at same dose level.
Grade 3	Hold* until \leq Grade 1. Reduce by 1 dose level.	Hold* until \leq Grade 1. Reduce by 1 dose level.
Grade 4	Hold* until \leq Grade 1. Reduce by 1 dose level.	Hold* until \leq Grade 1. Reduce by 1 dose level.
*Patients requiring a delay of all protocol therapy > 3 weeks due to toxicity should go off protocol therapy. ** After optimal anti-emetic therapy. Please refer to Section 8.6.1 . Use of prophylactic or scheduled antiemetics are recommended in future cycles for patients experiencing grade 2 or higher vomiting.		

Diarrhea**	Abemaciclib	LY3214996
≤ Grade 1	No change in dose.	No change in dose.
Grade 2 (1st episode)	Hold* until ≤ Grade 1. Resume at same dose level.	Hold* until ≤ Grade 1. Resume at same dose level.

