Grade 2 (Persistent or recurrent following resumption of therapy)	Hold* until ≤ Grade 1. Reduce by 1 dose level.	Hold* until ≤ Grade 1. Reduce by 1 dose level.
Grade 3	Hold* until ≤ Grade 1. Reduce by 1 dose level.	Hold* until ≤ Grade 1. Reduce by 1 dose level.
Grade 4	Hold* until ≤ Grade 1. Reduce by 1 dose level.	Hold* until ≤ Grade 1. Reduce by 1 dose level.
*Patients requiring a delay of all protocol therapy > 3 weeks due to toxicity should go off protocol therapy. ** After optimal anti-diarrheal therapy. Please refer to Section 8.6.1 . Use of prophylactic or scheduled anti-diarrheals are recommended in future cycles for patients experiencing grade 2 or higher diarrhea.		

Hepatotoxicity is a known adverse drug reaction of abemaciclib. Additional information is in the IB. Should a patient experience ≥ Grade 2 increase in AST and/or ALT we recommend holding therapy with dosing guidelines below. Please follow AST, ALT, and total bilirubin at least weekly until ≤ Grade 1 prior to re-initiating study therapy. Liver function can be monitored more frequently per investigator discretion.

AST and/or ALT Elevations**	Abemaciclib	LY3214996
≤ Grade 1 (>ULN-3.0x ULN)	No change in dose.	No change in dose.
Grade 2 (>3.0-5.0 x ULN) (without increase in total bili > 2 x ULN)	Hold* until meets treatment criteria. Resume at same dose level.	Hold* until meets treatment criteria. Resume at same dose level.
Grade 2 (without increase in total bili >2 x ULN; recurrent or persistent)	Hold* until ≤ Grade 1. Reduce by 1 dose level.	Hold* until ≤ Grade 1. Reduce by 1 dose level.
Grade 3 (>5.0-20.0 x ULN) (without increase in total bili > 2 x ULN)	Hold* until ≤ Grade 1. Reduce by 1 dose level.	Hold* until ≤ Grade 1. Reduce by 1 dose level.
Grade 2 (with increase in total bili > 2x ULN)	Discontinue therapy	Discontinue therapy
Grade 3 (with increase in total bili >2 x ULN)	Discontinue therapy	Discontinue therapy
Grade 4 (>20.0 x ULN)	Discontinue therapy	Discontinue therapy
*Patients requiring a delay of all protocol therapy > 3 weeks due to toxicity should go off protocol therapy. ** Use ULN unless baseline is greater than ULN, then use baseline for grading.		

Interstitial lung disease (ILD)/pneumonitis has been identified as an adverse drug reaction for abemaciclib. Additional information is available in the IB.

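### For diarrhea unresolved after 24 hours of treatment, Section 8.6.1.2 suspends and resumes abemaciclib only and omits LY3214996, whereas the Appendix 4 diarrhea table holds both drugs from Grade 2 upward

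*Combined protocol and SAP*

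**What the plan says.** Section 8.6.1.2 (Supportive Management for Diarrhea) has the patient start an anti-diarrheal at the first loose stool and contact the site, which assesses response within 24 hours. If the diarrhea has not come down to baseline or Grade 1 by then, "abemaciclib should be suspended until diarrhea is resolved to either baseline or at least Grade 1". The next bullet covers restarting: "When abemaciclib resumes, dosing should be adjusted as outlined in" Appendix 4. Both bullets name abemaciclib alone. LY3214996 appears nowhere in Section 8.6.1.2 or in its loperamide subsection, 8.6.1.2.1.

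The diarrhea table in Appendix 4 has a column for each drug. At Grade 1 or below neither dose changes. Every row from Grade 2 upward holds both drugs until Grade 1 or lower. The table carries the footnote "After optimal anti-diarrheal therapy. Please refer to Section 8.6.1".

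Section 8.3 sends the reader to Appendix 4 for dose adjustment, asks the investigator to attribute the toxicity first, and adds: "If the toxicity is not clearly attributable to either individual study drug, then the causality should be attributed to both study drugs". It also states: "If a dose adjustment is made, the patient must be maintained at the reduced dose level for all remaining cycles".

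Section 8.6.1.2.1 allows a one-level abemaciclib reduction to be considered for Grade 2 diarrhea that occurs despite loperamide, before further loperamide is given. It mentions no hold and does not separate first from repeat episodes.

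**The concern.** A treating physician managing diarrhea will naturally turn to the section written for diarrhea. That section gives a trigger, an action and a restart rule, so it reads as a complete instruction, yet it covers one of the two study drugs. Its neighbours name both drugs when both are meant: Table 8.1 does so for Grade 3 and Grade 4 rash, and Section 8.6.1.4 does so when growth factors are needed. Against that pattern, silence on LY3214996 can be taken as intended.

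Continuing LY3214996 by oversight matters. Section 3.1.2.1.2 says: "Expected overlapping toxicities of the combination include nausea, vomiting, fatigue, diarrhea". Section 3.2.1.5 gives creatinine increase, acute kidney injury and dehydration as the most common events leading to dose-limiting toxicity with daily single-agent LY3214996, and Section 8.6.1 warns of dehydration from vomiting and diarrhea.

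The lesser issue is the dose after a first Grade 2 episode. One physician may hold both drugs and resume both unchanged under Appendix 4. Another may lower abemaciclib without a hold under Section 8.6.1.2.1, and under Section 8.3 that reduction lasts for all remaining cycles.

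**Working it through.** The plan gives no figure to reproduce on this point. The check is a comparison of texts, followed by a count of what LY3214996 contributes.

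**1. Same clinical situation.** The Section 8.6.1.2 trigger is diarrhea above baseline and above Grade 1 after 24 hours of anti-diarrheal therapy, which means Grade 2 or higher on treatment. Appendix 4 grades diarrhea after optimal anti-diarrheal therapy. A patient who meets the trigger, once therapy counts as optimal, falls in one of the four rows below.

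**2. Actions side by side.**

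| Situation | Source | Abemaciclib | LY3214996 |
|---|---|---|---|
| Unresolved at 24 hours | 8.6.1.2 | Suspend; resume per Appendix 4 | Not mentioned |
| Grade 2, first episode | Appendix 4 | Hold; same dose | Hold; same dose |
| Grade 2, persistent or recurrent | Appendix 4 | Hold; down one level | Hold; down one level |
| Grade 3 | Appendix 4 | Hold; down one level | Hold; down one level |
| Grade 4 | Appendix 4 | Hold; down one level | Hold; down one level |
| Grade 2 despite loperamide | 8.6.1.2.1 | One-level reduction may be considered; no hold stated | Not mentioned |

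In Appendix 4, 4 of 4 rows at Grade 2 or above hold both drugs, 1 of 4 resumes both at the same dose, and 3 of 4 reduce both by one level.

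**3. Can one action satisfy both texts?** Yes. Section 8.6.1.2 does not tell anyone to continue LY3214996, so holding both drugs complies with it and with Appendix 4. Holding abemaciclib alone complies with the words of Section 8.6.1.2 but not with the table. The gap is an omission.

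**4. Does LY3214996 contribute to diarrhea?** Inputs are the related-diarrhea rows of Table 3.2 for the parts without abemaciclib.

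| Part | N | Any grade | Grade 3 or higher |
|---|---|---|---|
| A | 36 | 11 | 1 |
| A2 | 18 | 4 | 0 |
| B | 27 | 12 | 1 |
| Sum | 81 | 27 | 2 |

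- Any grade: 27/81 = 33.3%, exact (Clopper-Pearson) 95% CI 23.2% to 44.7%.
- Grade 3 or higher: 2/81 = 2.5%, exact 95% CI 0.3% to 8.6%.
- Check against the printed totals: adding Parts C, D and JP gives 11+4+12+8+2+0 = 37 of 108 for any grade and 1+0+1+3+0+0 = 5 of 108 for Grade 3 or higher, as in the table.
- Second check: Parts A and A2 together give 15/54 = 27.8%, the figure Section 3.2.1.5 reports for its 54 patients.

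In the abemaciclib combination (Part C), Grade 3 or higher related diarrhea was 3/20 = 15%. Table 3.1 lists diarrhea among the dose-limiting toxicities at three combination dose levels, all with a higher daily LY3214996 dose than the 200 mg used here.

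**5. What the counts do not show.** They pool several doses and schedules, and part of Part B included midazolam, so the rate at 200 mg daily may differ. Attribution was made without a control group. Neither a Grade 2 rate nor a rate of diarrhea unresolved after 24 hours is given, so the number of patients exposed to the gap cannot be computed.

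**The case against.** A reader might infer that the protocol orders LY3214996 to continue, or that two sections lay down contradictory rules. The documents do not support that. Section 8.6.1.2 is silent on LY3214996, its opening cites Appendix 4 without limiting it to one drug, and Section 8.3 gives Appendix 4 the dose-adjustment role. This part of the objection stands.

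A reader might also call the cross-references circular, because the Appendix 4 footnote points back to Section 8.6.1. That reference follows the words on optimal anti-diarrheal therapy and is most naturally a pointer to the supportive measures. The division of roles can be read from the text, although no sentence states that Appendix 4 prevails.

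Next, holding abemaciclib alone could be defended under Section 8.3 when the investigator clearly attributes the diarrhea to abemaciclib. That is plausible in some patients: Section 3.1.2.1.1 reports diarrhea in 90.2% on single-agent abemaciclib at 200 mg twice daily, above the 150 mg used here. But the Appendix 4 diarrhea table carries no attribution condition, and Section 8.6.1.2 does not tie its abemaciclib-only hold to attribution.

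Finally, the loperamide sentence may look like a conflict with Appendix 4. It is permissive, and it may describe a step before therapy is optimal, so the two may be successive stages. If Grade 2 persists, the 24-hour rule still suspends abemaciclib. The general Appendix 4 rule for intolerable Grade 2 toxicity also allows a one-level reduction, but only after withholding treatment, and whether it reaches diarrhea is not stated. What remains is that the order of steps is not spelled out.

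Practical risk is further limited by the 24-hour site contact and by the weekly review of toxicities and dose adjustments in Section 13.

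**Conclusion.** The concern holds as an incomplete instruction that does not match the protocol's own dosing table. Severity is minor. The exposure is confined to a physician who acts on Section 8.6.1.2 without opening Appendix 4 and so leaves LY3214996 running through diarrhea of Grade 2 or higher. The phase 1 counts support only the statement that LY3214996 is itself associated with diarrhea; they do not measure how often the gap would bite. The loperamide point is secondary and depends on reading Sections 8.6.1.2.1 and Appendix 4 as applying at the same stage of therapy, which the text leaves open. The conclusion assumes that Appendix 4 expresses the intended rule, as Section 8.3 indicates. Sample size, the primary test and the analysis plan are unaffected.

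**What to change.** In Section 8.6.1.2, state that abemaciclib and LY3214996 should be suspended when diarrhea is unresolved at 24 hours, and that both resume as set out in Appendix 4. State once that Appendix 4 governs holds and dose levels for diarrhea, including any reduction considered under Section 8.6.1.2.1. The loperamide sentence need not be deleted.

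The cost is protocol wording only, with no change to sample size, visits or analysis. The one drawback is that the text would leave no latitude to hold abemaciclib alone when diarrhea is clearly attributed to it. The Appendix 4 table already provides none. If the sponsor wants that latitude, it should be written into the table as an explicit exception.

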8.6.1.3 Supportive Management Recommendations for Nausea and Vomiting

Approximately 90% of patients have experienced nausea and/or vomiting due to LY3214996, which in a limited number of cases has led to more severe adverse events (i.e., dehydration, acute kidney injury). Therefore, patients will be required to receive antiemetic prophylaxis in cycle 1, in an effort to improve patient safety and reduce the incidence of these events. Recommended antiemetic treatment should follow current guidelines for high/moderate emetic risk agents, such as consensus-based guidelines from the National Comprehensive Cancer Network, but is left to investigator’s discretion based on patient characteristics and local medical practices.

Current recommendation for antiemetic treatment consists of a 5-HT₃ receptor antagonist and should be given prior to starting study drug (continue daily, choose 1):

- Ondansetron 8-16 mg (total dose) PO daily
- Dolasetron 100 mg PO daily, as needed

Breakthrough treatment can be given by adding 1 agent from a different drug class to the current regimen (i.e., olanzapine 5-10 mg PO daily, dexamethasone 12 mg PO/IV daily).

In the event that the investigator believes concomitant antiemetic medication is not necessary in cycles 2+, the antiemetic regimen may be discontinued.

Caution should be taken when administering medications that are metabolized by CYP3A4 when given with LY3214996 due to the potential inhibition of CYP3A4 metabolism by LY3214996 that could result in increased exposures of the co-medications. If possible, alternate medications that are not reliant on CYP3A4 metabolism for elimination should be utilized whenever possible.

8.6.1.4 Growth Factor Therapy

Growth factors should not be administered to a patient to satisfy study inclusion criteria. Growth factors may be administered in accordance with ASCO guidelines (Smith et al. 2015). Dosing of abemaciclib and LY3214996 must be suspended if the administration of growth factors is required and must not be recommenced within 48 hours of the last dose of growth factors having been administered. Following the administration of growth factors, the dose of abemaciclib must be reduced by 1 dose level on recommencement, if a dose reduction for the specific event necessitating the use of the growth factors has not already occurred.

